### Concomitant medication review

Data concerning concomitant medications and procedures will be collected throughout the trial, as specified in the [Flow Chart](#). These data will be obtained at scheduled or unscheduled trial visits provided spontaneously by the patient or as a result of questioning the patient.

## **6.2.3 Follow up period and trial completion**

For all patients, termination of trial medication and trial completion must be recorded on the corresponding eCRF.

For patients completing the safety FU period, the EOS visit is scheduled at 16 weeks after the last dose of study drug, ie at week 24 for those discontinuing after completing 12 weeks of treatment.

All patients completing the study will be offered to enter open label trial 1368-0017 or 1368-0020 respectively, where responders will receive SC maintenance treatment, while non-responders undergo i.v. re-induction. These patients are not requested to complete follow up period and will have their EOS visit at visit V6, co-inciding with the BL visit and start of study drug administration in 1368-0017 or 1368-0020 respectively.

Early treatment discontinuation

Patients who terminate study drug early should be encouraged to follow all study procedures per the [Flow Chart](#) until week 12, but not receive any more study drug at the respective visits. Given the patient's agreement, the patient will undergo the procedures for early treatment discontinuation and follow up as outlined in the [Flow Chart](#) (FC) and [Section 6.2.3](#).

Further treatment after the end of the trial

At the end of the trial, patients will be treated for their UC at the discretion of the investigator, according to local UC guidelines (e.g. ECCO guideline [R17-0243](#)).

Trial completion:

Trial completion is defined as a patient having reached the EOS visit. EOS visit will be at week 12 (V6) for patients rolling-over into subsequent maintenance trial; and at week 24 for patients who will not enter subsequent maintenance trial.

Regarding instructions for drug administration at missed or delayed visits, please refer to [Section 4.1.4](#).

## 7. STATISTICAL METHODS AND DETERMINATION OF SAMPLE SIZE

### 7.1 STATISTICAL DESIGN – MODEL

This trial is designed as a randomised, parallel-group, and double-blind, and placebo-controlled trial with 3 active doses of BI655130 (SPESOLIMAB) in Part 1 of the trial and 2 active doses of BI655130 (SPESOLIMAB) in Part 2 of the trial in patients with moderate to severe ulcerative colitis who have failed previous biologic treatments in the past.

The trial consists of 2 parts (cf. [Section 3.1](#)) which, for the purpose of statistical analyses, will be treated as two independent parts whereby the false positive rate is separately controlled within each trial part:

Part 1: To demonstrate proof of concept of clinical activity as an induction therapy on the primary endpoint of clinical remission at week 12 with respect to achieving a non-flat dose response curve, and subsequently to define suitable dose regimens for BI655130 (SPESOLIMAB) regarding efficacy and safety for further pivotal testing in part 2 of this trial. For this purpose, a multiple comparison procedure with modelling techniques (MCPMod) approach is considered.

Part 2: to confirm the efficacy and safety of two different doses of BI655130 (SPESOLIMAB) versus placebo as an induction therapy. Formal statistical hypothesis testing will be performed at an overall 1-sided alpha level of 0.025.

Each trial part will be analyzed independently of the remaining trial part, i.e.

- Only patients randomized into part 1 will be included in the analyses of part 1,
- Only patients randomized into part 2 will be included in the confirmatory analyses of part 2

In order to describe the full efficacy, safety and tolerability profile of BI655130 (SPESOLIMAB) in the population of patients with moderate to severe ulcerative colitis who have failed previous biologic treatments in the past, a pooled efficacy and safety analysis by dose group will also be generated, if at least one of the BI655130 (SPESOLIMAB) doses is identical in both study parts.

Note that statistical testing will be performed based on one-sided hypotheses and p-values. For publication purposes also two sided p-values will be derived; details of this will be specified in the TSAP.

Decision criteria for determining the achievement of proof of concept and subsequent dose selection criteria for the two doses of BI655130 (SPESOLIMAB) that will be studied in Part 2 of the trial are described in [Section 3.1.2](#).

Randomization for parts 1 and 2 will be stratified based on

- previous BIO treatment failure ( (TNF $\alpha$  antagonists-**OR**-Vedolizumab) versus (TNF $\alpha$  antagonists-**AND**-Vedolizumab) ) and
- concomitant corticosteroid therapy at visit 2/randomization (yes/no)
- Japan versus non-Japan  
To assure that sufficient patients per treatment group are recruited specifically to support individual country submission in Japan; this strata will be treated as an operational strata and will not be included into the analyses of the primary endpoint.

In addition, due to the low number of patients to be recruited into part 1 of this trial, the primary analysis of this part will be performed without consideration of stratification.

The proportion of patients who achieve clinical remission at Week 12 is the primary efficacy endpoint for each part of this trial. Clinical remission is defined as achieving an RBS = 0, an SFS = 0 or = 1 if there is a corresponding decrease  $\geq 1$  from baseline, as well as a modified ESS  $\leq 1$ , each of these components being measured as a part of the modified Mayo Clinical Score (mMCS). Colonoscopy and sigmoidoscopy images will be centrally read by an external independent assessor(s); images will also be read locally. The primary analysis will be performed using the centrally-read endoscopy scores; only if centrally-read data are missing will the local endoscopy score be used instead.

Considering the binary nature of the primary endpoint, this trial is designed to show an increase in the proportion of patients who demonstrate clinical remission for BI655130 (SPESOLIMAB) relative to Placebo. The primary analysis method for the confirmatory part of this trial (Part 2) will be the Cochran-Mantel-Haenszel risk difference estimation stratified by the randomization factors of previous BIO treatment failure and concomitant corticosteroid therapy at visit 2/randomization.

## 7.2 NULL AND ALTERNATIVE HYPOTHESES

The null and alternative hypotheses are described below separately for each trial part.

### Part 1

The null hypothesis is that there is a flat dose response curve comparing the placebo and the BI655130 (SPESOLIMAB) dose groups. The alternative hypothesis is that there is a non-flat dose response curve indicating a benefit of BI655130 (SPESOLIMAB) over Placebo.

The MCPMod procedure allows for simultaneous evaluation of different potential dose response patterns, whilst protecting the overall probability of Type I error (one sided  $\alpha$  of 20%). The pre-specified models and their parameters used for this test are outlined in [Section 7.3.1](#) and [Section 7.7](#).

### Part 2

Two doses of BI655130 (SPESOLIMAB) are planned to be investigated in this trial part; a low dose and a high dose. The exact doses to be included are dependent upon the outcome of

trial analysis on part 1 and the subsequent application of decision criteria as described in [Section 3.1.2](#).

This part of the trial is designed to confirm that at least one of two selected doses of BI655130 (SPESOLIMAB) is superior to placebo in achieving clinical remission at Week 12 in patients with moderate to severe ulcerative colitis who have failed previous biologic treatments in the past.

The null and alternative hypotheses for each of these two tests on the primary endpoint are described as follows:

(1) BI655130 (SPESOLIMAB) low dose vs. Placebo

$H_{0,11}$ : Effect of BI655130 (SPESOLIMAB) low dose on clinical remission at week 12  $\leq$  Placebo;  
versus  
 $H_{A,11}$ : Effect of BI655130 (SPESOLIMAB) low dose on clinical remission at week 12  $>$  Placebo.

(2) BI655130 (SPESOLIMAB) high dose vs. Placebo

$H_{0,12}$ : Effect of BI655130 (SPESOLIMAB) high dose on clinical remission at week 12  $\leq$  Placebo;  
versus  
 $H_{A,12}$ : Effect of BI655130 (SPESOLIMAB) high dose on clinical remission at week 12  $>$  Placebo.

Further hypotheses will be tested on the family of secondary endpoints in a hierarchical manner. The overall testing strategy used to control the type I error for each of the endpoints and for each of the treatments is described below. The null and alternative hypotheses for each of the two tests on each of the secondary endpoints are described as follows.

For Mucosal Healing at week 12

(3) BI655130 (SPESOLIMAB) low dose vs. Placebo

$H_{0,21}$ : Effect of BI655130 (SPESOLIMAB) low dose on mucosal healing at week 12  $\leq$  Placebo;  
versus  
 $H_{A,21}$ : Effect of BI655130 (SPESOLIMAB) low dose on mucosal healing at week 12  $>$  Placebo.

(4) BI655130 (SPESOLIMAB) high dose vs. Placebo

$H_{0,22}$ : Effect of BI655130 (SPESOLIMAB) high dose on mucosal healing at week 12  $\leq$  Placebo;  
versus  
 $H_{A,22}$ : Effect of BI655130 (SPESOLIMAB) high dose on mucosal healing at week 12  $>$  Placebo.

For the Clinical Response at week 12

(5) BI655130 (SPESOLIMAB) low dose vs. Placebo

$H_{0,31}$ : Effect of BI655130 (SPESOLIMAB) low dose on clinical response at week 12  $\leq$  Placebo;

versus

$H_{A,31}$ : Effect of BI655130 (SPESOLIMAB) low dose on clinical response at week 12  $>$  Placebo.

(6) BI655130 (SPESOLIMAB) high dose vs. Placebo

$H_{0,32}$ : Effect of BI655130 (SPESOLIMAB) high dose on clinical response at week 12  $\leq$  Placebo;

versus

$H_{A,32}$ : Effect of BI655130 (SPESOLIMAB) high dose on clinical response at week 12  $>$  Placebo.

For the change from baseline in IBDQ at week 12

(7) BI655130 (SPESOLIMAB) low dose vs. Placebo

$H_{0,41}$ : Effect of BI655130 (SPESOLIMAB) low dose on change from baseline in IBDQ at week 12  $\leq$  Placebo;

versus

$H_{A,41}$ : Effect of BI655130 (SPESOLIMAB) low dose on change from baseline in IBDQ at week 12  $>$  Placebo.

(8) BI655130 (SPESOLIMAB) high dose vs. Placebo

$H_{0,42}$ : Effect of BI655130 (SPESOLIMAB) high dose on change from baseline in IBDQ at week 12  $\leq$  Placebo;

versus

$H_{A,42}$ : Effect of BI655130 (SPESOLIMAB) high dose on change from baseline in IBDQ at week 12  $>$  Placebo.

For the combined Mucosal Healing and Histologic Remission at week 12

(9) BI655130 (SPESOLIMAB) low dose vs. Placebo

$H_{0,51}$ : Effect of BI655130 (SPESOLIMAB) low dose on combined Mucosal Healing and Histologic Remission at week 12  $\leq$  Placebo;

versus

$H_{A,51}$ : Effect of BI655130 (SPESOLIMAB) low dose on combined Mucosal Healing and Histologic Remission at week 12  $>$  Placebo.

(10) BI655130 (SPESOLIMAB) high dose vs. Placebo

$H_{0,52}$ : Effect of BI655130 (SPESOLIMAB) high dose on combined Mucosal Healing and Histologic Remission at week 12  $\leq$  Placebo;

[figure not shown]
[figure not shown]
versus

$H_{A,52}$ : Effect of BI655130 (SPESOLIMAB) high dose on combined Mucosal Healing and Histologic Remission at week 12  $>$  Placebo.

Overall the testing strategy will follow a closed testing principle defining two families of endpoints/comparisons. The first family consists of the primary endpoint comparison for both doses of BI655130 (SPESOLIMAB) vs placebo, whereas the second family is defined by the key-secondary (mucosal healing and clinical response) and secondary endpoints (change from baseline in IBDQ, and combined Mucosal Healing and Histologic Remission) comparisons for both doses of BI655130 (SPESOLIMAB) vs placebo.

Regarding the first family, to control the overall type I error rate at a 1-sided 0.025 alpha significance level for both of these two treatment comparisons on the primary endpoint at week 12, the (truncated) Hochberg method will be applied. The weight of the truncated Hochberg method is chosen as 0.5. Therefore, if both primary endpoint p-values are  $\leq 0.01875$  (one-sided), then both comparisons involving the two BI655130 (SPESOLIMAB) dose regimens will be declared statistically significant. If the maximum of the p-values for the two dose comparisons is  $> 0.01875$  (one-sided), then the other p-value will be tested at the 0.0125 one-sided level and declared to be statistically significant only if that p-value is  $\leq 0.0125$  (one-sided). The remaining alpha,  $\alpha'$ , to be used in the second family will be 0.025 (one-sided) if both primary endpoints show significance. If only one comparison is significant then  $\alpha'$  will be  $0.025/4=0.00625$  according to the truncated Hochberg procedure with weight of 0.5. If neither dose is declared to be statistically significant for the primary endpoint, then no further testing can be conducted.

[figure not shown]
If both doses of BI655130 (SPESOLIMAB) on the primary endpoint are declared to be statistically significant, then the following graphical procedure will be used to attribute the remaining  $\alpha'$  to the testing of each of the (hierarchically-ordered) key-secondary and secondary endpoints as follows:

If both doses are Significant on primary

One-sided alpha=  $\alpha' = \alpha = 0.025$

[figure not shown]
Note: H=High dose of BI655130 (SPESOLIMAB); L=Low dose of BI655130 (SPESOLIMAB); P=Placebo

If both doses of BI655130 (SPESOLIMAB) show significance in the first family, then the remaining alpha ( $\alpha'=0.025$ , one-sided) to be used in the secondary family will be equally split between the two doses of BI655130 (SPESOLIMAB) leading to an initial  $\alpha$  of 0.0125 per comparison. The test of a subsequent secondary endpoint in the hierarchical sequence, for a particular dose of BI655130 (SPESOLIMAB), is only performed if the test of the previous secondary endpoint on that same dose was successful. If, for one of the doses of BI655130 (SPESOLIMAB), the test on each of the endpoints (primary, key secondary, and secondary) is successful, then the remaining alpha may be passed to the secondary endpoint comparisons regarding the other dose leading to an initial level of 0.025 (one-sided).

[figure not shown]
If only one of the doses of BI655130 (SPESOLIMAB) on the primary endpoint is declared to be statistically significant, then the following graphical procedure will be used to attribute the remaining  $\alpha'$  to the testing of each of the (hierarchically-ordered) key-secondary and secondary endpoints as follows:

Truncated Hochberg with 'truncation fraction' = 1/2  
 One-sided alpha level =  $\alpha$

If only one dose is Significant on primary  $\downarrow$  One-sided alpha =  $\alpha' = \alpha/4 = 0.00625$

Note: H=High dose of BI655130 (SPESOLIMAB); L=Low dose of BI655130 (SPESOLIMAB); P=Placebo; BI= the single dose of BI655130 (SPESOLIMAB) that was successful on the test of the primary endpoint (low or high dose)

If only one dose of BI655130 (SPESOLIMAB) shows statistical significance in the first family, then the tests for the secondary family will only be performed with respect to the comparisons involving the same dose of BI655130 (SPESOLIMAB) for which the primary endpoint was successful, utilizing the remaining alpha ( $\alpha'=0.00625$ , one-sided) transferred from the primary family. In this case, there will be no alpha passing to the other dose even if all tests on the secondary endpoints are successful.

(Simulation-based) power calculations with respect to the planned sample size and the chosen testing strategy for the primary analysis can be found in [Sections 7.7.1](#) and [7.3.1](#) respectively.

### 7.3 PLANNED ANALYSES

There will be 4 main patient populations in this trial for analyses: the randomized set (RS), the safety analysis set (SAF), the modified RS (m-RS), and the per-protocol set (PPS). Each of these populations will be derived separately for each of the 2 trial parts.

#### Randomized Set (RS)

This patient set includes all randomized patients. Treatment assignment will be as randomized. This is the main analysis set for presentation of efficacy on binary endpoints.

#### Safety Analysis Set (SAF)

This patient set includes all patients who were randomized and received at least one dose of study drug. It will be the main analysis set for presentation of safety. Patients will be analyzed according to the actual treatment.

#### Modified Randomized Set (m-RS)

This patient set includes all patients in the RS who had a baseline and at least one post-baseline measurement for the endpoint under consideration. Treatment assignment will be as randomized. This is the main analysis set for presentation of efficacy on continuous data, e.g. IBDQ.

#### Per-Protocol Set (PPS)

This patient set includes all patients in the RS who adhered to the CTP without any IPVs (potentially affecting the study outcome) which lead to exclusion from the PPS. This set will be used for sensitivity analysis on the primary efficacy endpoint.

Further analysis sets, e.g. for the BM assessments, will be defined in the TSAP.

Important violations of the protocol will include violations of the key inclusion and exclusion criteria, incorrect medications taken, concomitant use of restricted medications, and any other violations of the protocol deemed important by the study team. All decisions concerning important protocol violations will be made prior to un-blinding of the database for the respective trial part.

Standard statistical parameters (number of non-missing values, mean, standard deviation (SD), median, quartiles, minimum and maximum) or frequency tables (including patient frequencies and percentages) will be calculated where appropriate.

The following analyses of this trial protocol, in chronological order, are planned:

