#### **4.1.5 Blinding and procedures for unblinding**

##### **4.1.5.1 Blinding**

For Part 1 of the study, patients, investigators, as well as sponsor personnel involved in the trial conduct or analysis, will remain blinded with regard to the randomised treatment assignments until after the database lock for the final week 12 analysis on Part 1 has been performed. At this time, all dosing visits will have been completed, although some patients who did not roll-over directly into the maintenance trial (1368-0017) will continue the safety follow-up. Since the final analysis of part 1 of the trial in terms of both efficacy and safety will be complete, and because no further patient dosing visits are planned in this trial part, the randomization codes for part 1 will be formally unblinded subsequent to the week 12 database lock, and the part 1 trial results will be published to support enrolment into part 2 of the study.

For Part 2 of the study, patients, investigators, as well as sponsor personnel involved in the trial conduct or analysis, will remain blinded with regard to the randomised treatment assignments until after the database lock for the final analysis on part 2 of the current trial has been performed. Once the database lock has been performed, the sponsor will be officially unblinded to the randomization details for this trial part and the part 2 trial results will be published to support enrolment into subsequent studies. Patients and investigators will continue to remain blinded to the individual treatment allocations in part 2 of the current trial through the end of the subsequent maintenance trial, 1368-0020. A logistics plan will be developed describing the mechanisms to be put in place to assure that the patients and investigators remain blinded to individual patient data, and which is to be finalized prior to the treatment unblind for the final analysis on Part 2.

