#### 7.4 INTERIM ANALYSES

In order to ensure the patient's safety during the trial, a fully external DMC (same DMC for both parts 1 and 2), independent of the trial and project teams, will be set-up to review all available un-blinded safety data as well as selected efficacy data at regular intervals following first-patient-in. A DMC SAP which describes the analyses required for assessment by the DMC will be produced and finalized prior to first patient randomised into the trial. Further details will be provided in a DMC charter.

No interim analyses of the primary endpoint(s) are planned for part 1 or for part 2 of the trial.

The primary analysis of Part 1 of the trial will be performed once all treated patients have completed the 12-week treatment period in this trial part; an interim data base snapshot will be done.

The primary analysis of Part 2 of the trial will be performed once all treated patients have completed this trial part.

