The first interim database snapshot and analysis of Part 1, will be performed based upon those randomized patients in Part 1 who have completed/discontinued through the planned first 12 weeks of trial up to the cut-off date (see [Section 6.3](#)). The following data will be used in this analysis:

- Selected summaries of the 12-Week data will be summarized up to the minimum of the (analysis-specific data cut-off; study day 99), unless otherwise specified.

For the second interim database snapshot (the primary analysis per the CTP), to be performed once all randomized patients have completed/discontinued through the planned first 12 weeks of trial (per CTP specification), the following data will be used:

- All 12-Week data will be summarized up to the minimum of the (analysis-specific data cut-off; study day 99), unless otherwise specified.

The final, updated analysis of the trial, will be performed once all patients have completed the trial. Generally only listings of the trial data are planned to be done, however, updates on the primary and secondary endpoint analysis, as well as select AE displays will be produced in order to confirm the consistency of the results to those results obtained at the previous interim snapshots. Any clinical relevant changes from the previous interim analyses to the final analysis will be addressed in the CTR.

Treatment groups for analysis are listed as follows:

- **"Placebo"**
- **"Speso 300 mg IV SD"**
- **"Speso 450 mg IV q4w"**
- **"Speso 1200 mg IV q4w"**
- **"Speso Total"** (across all BI treatment arms)
- **"Overall Total"**(across treatments), where appropriate.

"Overall Total" is applicable in disposition, demographics and baseline characteristics, compliance summaries and safety tables. "BI Total" should also be presented in safety tables.

More details on the technical implementation of these analyses are provided in the ADS Plan of this TSAP.

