D2.04	Concurrent UC treatments need to be on stable doses prior or up to Week 12: Probiotics (e.g. S. boulardii) LABEL: Probiotics not stable	Medical review	None	#
F	Study specific analysis			
F1	Other trial specific violation			
F1.01	Incomplete diagnosis of ulcerative colitis LABEL: Incomplete diagnosis of UC	Medical review	PPS	#
F1.02	Primary endpoint assessment more than 2 weeks before planned day LABEL: Primary endpoint assessment > 2 weeks before planned.		PPS	
F2	Certain violations of procedures used to measure primary or secondary efficacy data	<not specified>		
G	Other safety related violations			
G1.01	Pregnancy test not done for woman of child bearing potential, or pregnant during study LABEL: Pregnancy test not done or pregnant	Pregnancy test not done at any visit where such is scheduled	None	

PV will be detected manually

For specification on definition of analysis sets, refer to Section 6.3. Analysis of efficacy data according to the PPS will be done at the time of the 2nd interim database snapshot only [including all randomized patients through week 12].

Source: BI reference document 'Identify and Manage Important Protocol Deviations (iPD)' [001-MCS-50-413] (4, 6).

¹ See [Section 6.3](#) for population definition

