The discussion of all exceptional cases and problems and the decisions on the allocation of patients to populations will be made at latest at the DBLM. A separate DBLM will be performed prior to each database snapshot of this trial.

Handling of Treatment Misallocations in Analysis Sets

If a subject is randomized but not treated, they will be reported under their randomized treatment group for efficacy analysis according to RS, m-RS, and PPS (per the intent-to-treatment principle). By definition, however, such patients are excluded from the safety analyses as no study medication was taken.

If a subject is treated but not randomized, they will be excluded from both efficacy analysis and safety analysis by definition. However, subjects under such circumstances will be summarized in the final clinical trial report.

If a subject is randomized but took incorrect treatment during the study, then:

- For efficacy analyses according to RS, m-RS, and PPS, they will be reported under their randomized treatment groups. But if the subject has an iPD as defined in [Section 6.2](#), the subject will be excluded from PPS for efficacy analysis.
- For safety analyses using the SAF,
 - if a subject is planned with multiple dose administrations of BI 655130 (randomized to 450mg q4w, 1200mg q4w), they will be reported under their randomized treatment group for safety analysis because the overall safety profile will be driven by the amount of drug received in totality over the entire treatment duration. It is not likely that the safety profile will deviate from the planned treatment regimen if the subject receives only one or two vials of the incorrect medication at only some dosing occasions.
 - if a subject is planned with a single dose administration of BI 655130 (randomized to 300mg SD), they will be reported under BI 655130 300mg SD if the subject receives at least one dose of BI 655130 at any visit. A subject will be assigned to the placebo treatment group only if they don't receive any BI 655130 during the entire treatment period.
 - if a subject is planned with placebo treatment, they will be reported under placebo if no treatment with BI 655130 is received at any visit. If the subject receives $> = 1$ vial ($> = 150$ mg) of BI 655130 during the entire treatment duration, they will be reported as BI 655130 300mg SD treatment group.

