[Table 6.3: 1](#) (first interim database snapshot), [Table 6.3: 2](#) (second interim database snapshot), and [Table 6.3: 3](#) (final trial snapshot) illustrates the data sets which are to be used

for each category class of endpoints, and the approaches used with regard to missing data. For explanation of the different methods of handling missing data see [Section 6.6](#).

Table 6.3: 1 Subject sets analysed (first interim database snapshot)

Class of endpoint	Patient set			
	ESi	RSi	SAFi	m-RSi
Disposition	√	√		
Compliance		√		
Exposure			√	
iPDs		n.a.		
Demographic/baseline characteristics		√		
Primary efficacy endpoint (primary analysis only)		√		
Secondary efficacy endpoints (Binary) (primary analysis only)		√		
Secondary efficacy endpoints (Continuous) (primary analysis only)				√
Safety parameters			√	
Use of rescue medication		√		

At the time of the first interim database snapshot, only selected analyses on each efficacy endpoint will be done. All safety displays will be produced.

Table 6.3: 2 Subject sets analysed (second interim database snapshot)

Class of endpoint	Patient set				
	ES	RS	SAF	m-RS	PPS
Disposition	√	√			
Compliance		√			
Exposure			√		
iPDs*		√			
Demographic/baseline characteristics		√			
Primary efficacy endpoint		√			√
Secondary efficacy endpoints (Binary)		√			
Secondary efficacy endpoints (Continuous)				√	
Safety parameters			√		
Use of rescue medication		√			

[figure not shown]
*the patient with iPD of treated but not randomized will only be listed in the footnote of the iPD table.

[figure not shown]
At the time of the second interim database snapshot, all analyses per TSAP are scheduled to be performed.

Table 6.3: 3 Subject sets analysed (final, updated trial snapshot)

Class of endpoint	Patient set			
	ES	RS	SAF	m-RS
Disposition	√	√		
Compliance		n.a.		
Exposure			n.a.	
iPDs		n.a.		
Demographic/baseline characteristics		n.a.		
Primary efficacy endpoint (primary analysis only)		√		
Secondary efficacy endpoints (Binary) (primary analysis only)		√		
Secondary efficacy endpoints (Continuous) (primary analysis only)				√
[REDACTED]				
Safety parameters (selected displays only)			√	
Use of rescue medication		n.a.		

At the time of the final, updated database snapshot, only select analyses of the trial data are to be performed in order to ensure the consistency in key trial conclusions subsequent to the performance of two interim database snapshots.

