7. PLANNED ANALYSIS

The following analyses are planned at different stages throughout Part 1 of this trial.

Part 1 – First Interim Database Snapshot - Week 12 Analysis

The analysis will be performed using all randomized patients who completed/ discontinued through the week 12 visit on or prior to the cut-off date (see Section 3). A database snapshot will then be done. At this time, an interim analysis of the efficacy and safety data through Week 12 will be performed by the sponsor.

The individual patient cut-off date for inclusion of data into the analysis is the minimum of the analysis-specific data cut-off, or study day 99, as described in [Table 6.7: 1](#).

The analyses as described in Section 6.3 of this TSAP will be performed using the subject sets of ESi, RSi, m-RSi, and SAFi.

Part 1 – Second Interim Database Snapshot - Week 12 Primary Analysis (All Randomized Patients)

The analysis will be performed using all randomized patients who completed/ discontinued through the week 12 visit. A database snapshot will then be done. At this time, the complete, primary analysis of all efficacy, safety, and PK/ADA data will be done through Week 12, and will be performed by the sponsor; biomarker data will be reported, if available.

The individual patient cut-off date for inclusion of data into the analysis is the minimum of the analysis-specific data cut-off, or study day 99, as described in [Table 6.7: 1](#).

The analyses as described in Section 6.3 of this TSAP will be performed using the subject sets of ES, RS, m-RS, SAF, and PPS.

Part 1 – Updated analysis after final DBL

A final database lock will be done when all randomized patients in Part 1 complete the trial. A majority of the trial patients are expected to roll-over into the extension trial at Week 12. The analyses as described in Section 6.3 of this TSAP will be performed, up to week 12, using the subject sets of ES, RS, m-RS, and SAF. Selected safety summaries including all data up to the REP, will also be generated.

General Remarks

The format of the listings and tables will follow the BI guideline "Reporting of clinical trials and project summaries" (001-MCG-159) ([9](#)).

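### The SAP allows per-protocol exclusions to be decided after the sponsor has seen results by arm at a first snapshot, although the protocol requires those decisions before unblinding

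*Protocol*

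**What the plan says.** **Protocol.** Section 7.3, under the Per-Protocol Set, fixes the order of events: "All decisions concerning important protocol violations will be made prior to un-blinding of the database for the respective trial part". Section 4.1.5.1 says that patients, investigators and the sponsor staff who conduct or analyse the trial "will remain blinded with regard to the randomised treatment assignments until after the database lock for the final week 12 analysis on Part 1". Section 7.3 places that analysis after every randomised patient has completed the first 12 weeks. Section 7.4 adds: "No interim analyses of the primary endpoint(s) are planned for part 1 or for part 2 of the trial".

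**SAP.** Version 3.0 was issued because the study was terminated early. Section 6.1 introduces a first snapshot based on "those randomized patients in Part 1 who have completed/discontinued through the planned first 12 weeks of trial up to the cut-off date". Section 7 says of it: "At this time, an interim analysis of the efficacy and safety data through Week 12 will be performed by the sponsor". Table 6.3: 1 includes the primary analysis of the primary endpoint on RSi, the first-snapshot subset of the randomised set. It has no PPS column and shows important protocol deviations (iPDs) as not applicable.

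The note to Table 6.2: 1 says: "Analysis of efficacy data according to the PPS will be done at the time of the 2nd interim database snapshot only". Section 6.3 sets the database lock meeting (DBLM) as the latest point for allocating patients to sets, and adds: "A separate DBLM will be performed prior to each database snapshot of this trial".

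**The concern.** A per-protocol analysis is useful as a check only if nobody who decides the exclusions knows how the arms are doing. The protocol secures this by putting all such decisions before unblinding. Once the SAP places an unblinded, sponsor-run analysis before the last allocation meeting, that safeguard no longer follows from the sequence of events. It has to be stated, and the visible SAP does not state it.

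What is at stake is the credibility of the PPS sensitivity analysis. If it agrees with the primary analysis, a reader cannot exclude that knowledge of the arms shaped the set. If it disagrees, the same doubt applies in the other direction.

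**Working it through.** No formula applies. The check compares the order of events in the two documents.

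1. **Order under the protocol (4.1.5.1, 7.3, 7.4).** All violation decisions; one week 12 lock covering all randomised patients; unblinding; analysis.

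2. **Order under the SAP (3, 6.1, 6.2, 6.3, 7).** First DBLM; first snapshot with the sponsor's primary analysis on RSi; second DBLM; second snapshot with the PPS analysis on all randomised patients.

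3. **Is the first snapshot unblinded?** Yes, on the visible text. SAP 3 ties the logistics and access plan to a database snapshot and the unblinding of treatment. The primary analysis in SAP 7.4 is MCP-Mod, which estimates a remission rate for each dose group and so needs the treatment codes.

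4. **Whose PPS status can still be open afterwards?**
   - *Patients in RSi.* A DBLM precedes the first snapshot, so their status could be closed there. Nothing requires it, because no PPS is used at that snapshot.
   - *Patients not yet through week 12 at the cut-off.* Entries D1.01 and D2.01 to D2.03 cover medication up to week 12. They cannot be fully judged until after the first analysis.

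5. **Are the open decisions judgements?** In Table 6.2: 1, nine entries that exclude from the PPS carry the mark for manual detection: A1.03, A1.06, GI.04, C4.01, D1.01, D2.01, D2.02, D2.03 and F1.01. The mark describes how a deviation is found and does not by itself prove discretion. The comments go further:
   - A1.06 and GI.04 allow later medical review to add an exclusion that the case report form did not show.
   - D2.01 to D2.03 depend on medical review of whether a dose increase was given as rescue.
   - D1.01 depends on whether a restricted medication was given as rescue.

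6. **Which decisions cannot come before unblinding?** C1.01 and C1.02 (wrong trial medication) need the treatment codes, and the SAP says so. Their criteria are counts of vials, so they can be applied afterwards without judgement.

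7. **What does the PPS feed?** Protocol 7.3 and SAP 6.3 use it for a sensitivity analysis of the primary endpoint. The primary analysis uses the randomised set, with missing outcomes counted as non-response.

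Steps 1 and 2 conflict, and steps 3 to 5 show that the conflict reaches decisions open to judgement.

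**The case against.** **Much of the safeguard may already exist.** The exclusion criteria are pre-specified in Table 6.2: 1. A DBLM precedes the first snapshot. SAP 3 promises a logistics and access plan to protect the blind and the integrity of the ongoing trial. All of this stands, and the plan may well keep the people who judge deviations away from the codes. But the plan is not visible, and the visible SAP neither closes RSi decisions at the first meeting nor says that those who judge the rest stay blinded.

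**Early termination explains the change.** This also stands. The protocol predates the SAP revision and does not mention termination. SAP Section 4, which is meant to list changes to the planned analysis, shows no text in the public copy, and part of Section 3 is missing too. A reader might infer an undeclared departure from the protocol. The documents do not support that.

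**The not-applicable entry for iPDs in Table 6.3: 1.** A reader might take it to mean that deviation review is skipped at the first snapshot. It more naturally concerns displays: Table 6.3: 3 uses the same entry for compliance, exposure and baseline characteristics.

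**Two looks at proof of concept.** A reader might infer that testing at both snapshots at one-sided 20% inflates the false positive rate. The documents do not support this. SAP 6.1 and 7 name the second snapshot as the primary analysis, Section 7 presents its analyses for that snapshot with only a selection at the first, and SAP 7.4 bases the primary analysis on the full randomised set. No visible rule lets RSi establish proof of concept.

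**Conclusion.** The point holds as a conflict of sequence between Protocol 4.1.5.1 and 7.3 and SAP 6.2, 6.3 and 7. As visibly written, PPS exclusions that rest on manual or medical review can be decided after results by arm are known.

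Its reach is limited to the PPS sensitivity analysis. It cannot be sized: the visible text gives no cut-off date, no number of patients outside RSi and no expected number of exclusions. A reader might extend it to the primary analysis, because rescue use counts as non-response and the D2 entries depend on what was rescue. The visible text does not say when or by whom rescue is classified, and the protocol rule at issue covers violations, so the point is not carried that far.

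The conclusion assumes that the first snapshot is unblinded to sponsor staff who may also judge deviations. If the access plan already separates them, what remains for patients outside RSi is a missing statement in the SAP.

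**What to change.** Amend SAP 6.2 and 6.3 as follows:

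1. All iPD and PPS decisions for patients in RSi are signed off at the DBLM before the first unblinding, apart from C1.01 and C1.02.
2. Decisions for the remaining randomised patients are made by staff without access to treatment codes or to any first-snapshot output.
3. C1.01 and C1.02 are settled after unblinding by applying their pre-specified vial-count rules mechanically, with no further review.

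As an optional clarification, one sentence in SAP 7.4 could say that proof of concept is judged only at the second snapshot.

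The cost is SAP wording and one blinded data review brought forward. No endpoint, analysis model or sample size changes.
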